4. SELECTION AND ENROLLMENT OF PARTICIPANTS

4.1. Facility Inclusion Criteria

Facility eligibility criteria include:

Matched facility ID on Brown University's list of all Medicare/Medicaid-certified nursing facilities in the U.S.

Serve both short and long-stay patients

Have >50 beds

Have an EMR system

Have at least 20 admissions and 20 annual Minimum Data Set (MDS) assessments (regardless of whether patients were discharged alive)

We anticipated that a total of approximately 360 (297 Genesis HealthCare / 63 PruittHealth) facilities would be eligible for random assignment.

4.2. Patient Inclusion Criteria:

As the ACP video intervention will be implemented facility-wide, all patients in eligible NHs during the 24-month implementation period are eligible. There are no exclusions based on age, gender, race, ethnicity, or clinical features.

Although the ACP intervention will be implemented facility-wide, its effectiveness will be examined among targeted NH sub-populations for Aims 2, 3, and 4. Target populations for these Aims include patients ≥ 65 in the NHs during the 24-month implementation period who meet the following eligibility definitions based on MDS assessments. For all three aims, residents will be eligible for the target sub-populations if they meet these criteria either at the start (prevalent cases) or during (incident cases) the 24-month implementation phase. Incident cases include new admissions and long-stay residents who "convert" over the implementation phase by meeting eligibility criteria based upon changes in their repeated MDS assessments.

Aim 2: Patients ≥ 65 who are in nursing home ≥ 90 days (long-stay) who have EITHER of the following two conditions:

1. *Advanced Dementia:* must have all three criteria: a, b, and c
 - a. Alzheimer's disease or other dementia
 - b. Advanced cognitive impairment*
 - c. Extensive or total assistance needed for eating and transferring

*Advanced cognitive impairment is defined as a score of 3 or 4 on the Cognitive Function Scale based on variables from the MDS Version 3.0^{119, 120}

2. *Advanced COPD/CHF:* must have all three criteria: a, b, and c
 - a. CHF/COPD
 - b. Shortness of breath sitting or lying flat
 - c. Extensive or total assistance walking in room, transferring, walking in corridor, locomotion on/off unit, or dressing.

Aim 3: Patients ≥ 65 who are in nursing home < 90 days (short-stay) who have advanced dementia OR advanced CHF/COPD as defined above.

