randomized to the control arm, and 3. Our partner health care systems strongly preferred post-randomization recruitment.

Once the intervention NHs are recruited, intervention training and implementation will be rolled out in a staggered fashion over the next 6 months (*see Section 5.2*), such that by month 8 of year 1, all intervention NHs will be up and running.

[figure not shown]
4.4.2. Facility Recruitment Estimates:

Based upon our sample size calculations, we require 103 facilities per arm (See section 9.2). To account for the fact that some (we estimated up to 10%) facilities randomized to the intervention arm would fail to participate fully in the intervention implementation (but will be included in our intention to treat analysis) we increased our facility recruitment targets by at least 10%, for a total of 119 facilities in the intervention study arm.

From the pool of eligible facilities, 119 will be randomly assigned to the intervention arm, and all the remaining eligible facilities (n=241) will be assigned to the control arm (approximate 2:1 control:intervention match). We will leave all non-intervention facilities in the control arm since there is no additional cost to do so and having the increased number of control facilities increased precision.

4.4.3. Facility Randomization and Stratification Procedures:

Facilities will be randomized using a stratified approach with two levels of stratification. The first stratum is the NH health care system (Genesis HealthCare and PruittHealth). Within each health system, the second stratum will be on the hospitalization rate as measured by # hospitalization/person-days alive for patients with advanced dementia or COPD/CHF in all NHs in each health care system in the prior 12 months based on MDS files available at Brown University. The rationale for this stratum is that hospitalization rates, the primary trial outcome, are known to vary considerably at the facility-level due to regional practice, market influences and underlying quality. Since inter-facility hospitalization rates vary quite broadly, facilities will be grouped into terciles to minimize the chance of misdistribution. After the second stratification level is applied, facilities will be randomly assigned to either the control or intervention arm by a statistician at Brown University. Immediately following random assignment, we will test the balance between the arms using all available facility and resident-level data.

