6.3 Data Elements

Data elements and sources are described below and in Table 2.

6.3.1. Facility-level data: Facility-level data are needed for facility recruitment, randomization, and descriptive purposes. Organizational data from OSCAR include: number of beds, for-profit status, and NH chain. Aggregated MDS data at Brown University provide information case-mix (% long-stay and post-acute care patients). MDS data are also used to calculate the hospitalization rate of each facility by estimating the number of patient days at risk of hospitalization from the nursing home and counting the number of actual hospital transfers to hospital per unit time. It is these hospital specific rates from the prior year which will be used to undertake the stratified randomization scheme (*see Section 4.4.2*). Medicare claims available at Brown University will be used to determine the facilities' hospitalization rates for the subset of patients with Medicare fee for service.

| Table 2: Data Element and Sources | | | | | |
|--|---|---------------|------------|-----------------|--------------|
| Data Element | Purpose | SOURCE | | | |
| | | EMR | MDS | Medicare | OSCAR |
| Facility-Level | | | | | |
| Organization | recruitment | | | | X |
| Case-mix | recruitment | | X | | |
| Prior Hospitalization rate | randomization | | X | | |
| | | | | | |
| Patient-Level | | | | | |
| Demographic | covariate | X | X | | |
| Long vs. short-stay | Cohort definition | | X | | |
| Functional status | target sub-population identification, covariate | | X | | |
| Cognitive status | target sub-population identification, covariate | | X | | |
| Medical condition | target sub-population identification, covariate | X | X | | |
| Insurance | covariate | | | X | |
| Advance directives | 2° outcome | X | | | |
| Health services use | 1° and 2° outcome | X | X | X | |
| Burdensome interventions | 2° outcome | X | X | X | |
| Death | description, competing risk | | X | X | |
| Intervention implementation | monitoring fidelity | X | | | |

6.3.2. Patient-level data:

6.3.2.a. Cohort description, identification of target sub-groups, and other independent variables

Demographic data: From MDS: Age, gender, race, ethnicity, religion, primary language, marital status, and length of NH stay.

Long-stay or new admission to post-acute care: From MDS.

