Using current MDS data from CMS, we observe that the distribution of the primary outcome, hospital transfers, is over-dispersed with many of the patients having no hospital transfer over the 12-month follow up period. In addition, we also observed that hospital transfer rates vary across facilities, even after adjusting for underlying patient risk. To account for these phenomena, we will utilize a zero-inflated Poisson distribution with facility random effects to test and estimate the effects of the ACP intervention. Zero-inflated Poisson models have been used in other public health settings.^{128, 129} Formally, let Y_{ij} be the number of hospital transfers for person i in facility j , N_{ij} is the number of person days alive for person i in facility j , and T_j is a treatment indicator that is equal to one if facility j is in the intervention group. Then where β_1 is the conditional increase in the log hospital transfer rate in facilities that receive treatment vs. those that do not, and α_1 is the conditional log odds ratio for being hospitalized vs. never being hospitalized in the intervention vs. the control arm. When both α_1 and β_1 are smaller than 0, the ACP video is effective in reducing the proportion of patients hospitalized and the number of times hospitalized. Using this model we will estimate the marginal average hospital transfer rate in each arm and calculate the difference between the two arms. We will use a two sided test to examine if the marginal average difference is significantly different than zero, and we will calculate the corresponding interval estimate. As a secondary analysis, we will use the likelihood ratio test to compare the null hypothesis, $H_0 : \alpha_1 = \beta_1 = 0$, to the alternative hypothesis $H_1 : \alpha_1 \neq 0$ or $\beta_1 \neq 0$.¹³⁰ Confidence intervals for α_1 and β_1 can be obtained by inverting the likelihood ratio test.¹³² This analysis will enable us to provide additional details as to whether the effectiveness of the intervention is to reduce the likelihood of one hospital transfer or the number of hospital transfers if transferred at least once.

The secondary outcomes are binary. Commonly used methods applied to the analysis of clustered RCT with binary outcomes are GEE and multilevel models.¹³¹ The former method provides a population “average” effect, while the latter results in a conditional cluster effect. For continuous Gaussian data, interpretation of the treatment coefficient

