$$\begin{aligned}
 p(Y_{ij} = 0) &= \phi_{ij} + (1 - \phi_{ij}) \exp^{-\theta_{ij}} \\
 P(Y_{ij} = y) &= (1 - \phi_{ij}) \frac{\exp^{-\theta_{ij}} \theta_{ij}^y}{y!} \quad y = 1, 2, \dots \\
 \text{logit}(\phi_{ij}) &= \alpha_0 + \alpha_1 T_j + u_j \quad u_j \sim N(0, \sigma_u^2) \\
 \text{log}(\theta_{ij}) &= \beta_0 + \beta_1 T_j + \log(N_{ij}) + v_j \quad v_j \sim N(0, \sigma_v^2)
 \end{aligned}$$

is the same in conditional and marginal models; however, with binary data, the treatment coefficient from a marginal model is smaller than that from a conditional model and has a different interpretation.¹³² For binary outcomes, Bellamy et al¹³³ have shown that with few clusters GEE results were more likely to reject the null hypothesis, while conditional models resulted in more conservative estimates. Austin concluded that the power of GEE and multilevel models are very similar for studies, like ours, that include more than 30 clusters (facilities) with either variable or equal cluster size.¹³⁴ To estimate the effect of ACP on secondary outcomes we will use random effects logistic model. Formally, let S_{ij} one of the secondary outcomes for person i in facility j , and T_j is a treatment indicator that is equal to one if facility j is in the treated arm.

$$\begin{aligned}
 S_{ij} &\sim \text{Ber}(p_{ij}) \\
 \text{logit}(p_{ij}) &= \gamma_0 + \gamma_1 T_j + \zeta_j \\
 \zeta_j &\sim N(0, \sigma_\zeta^2)
 \end{aligned}$$

where γ_1 is the conditional log odds ratio for observing the secondary outcome in the treatment arm vs. the control arm. When γ_1 is smaller than 0, ACP is effective. As for the primary outcome we will use the likelihood ratio test the null hypothesis $H_0 : \gamma_1 = 0$, and by inverting this test we will obtain the corresponding confidence interval.

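### The primary Aim 2 model has no terms for the six randomisation strata; if they are prognostic and allocation is about equal across them, the primary interval is too wide and the test conservative

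*Combined protocol and SAP*

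**What the plan says.** **Design.** Section 4.4.3 states: "Facilities will be randomized using a stratified approach with two levels of stratification". The first level is the health system. The second, within system, is the prior 12-month hospitalization rate in residents with the target conditions, from MDS files: "Since inter-facility hospitalization rates vary quite broadly, facilities will be grouped into terciles to minimize the chance of misdistribution". Section 6.3.1 confirms the use of the prior-year rate: "It is these hospital specific rates from the prior year which will be used to undertake the stratified randomization scheme". Section 4.1 expects "a total of approximately 360 (297 Genesis HealthCare / 63 PruittHealth) facilities would be eligible". Section 4.4.2 assigns 119 facilities to intervention and 241 to control overall. The split within each stratum is not given.

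**Analysis.** In 9.5 the log rate of the primary model is "\beta_0 + \beta_1 T_j + \log(N_{ij}) + v_j". The zero part has an intercept, treatment and a facility effect. The logistic model for secondary outcomes is "\gamma_0 + \gamma_1 T_j + \zeta_j". The primary test rests on a marginal contrast: "Using this model we will estimate the marginal average hospital transfer rate in each arm and calculate the difference between the two arms". How its variance is computed is not stated.

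**Elsewhere.** Section 9.1 allows adjustment for patient characteristics if needed. The Aim 4 transfer model has covariates that are not named. Section 9.6 uses facility covariates, but only in the supplemental as-treated models. A sentence in the précis, under Sample Size and Population, says that outcome analyses do not vary by stratum.

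**The concern.** Stratified assignment takes between-stratum differences out of the true sampling error of the arm contrast. A model without strata still counts those differences as facility variance, so its standard error is larger than the design warrants. The estimate itself is about equally variable either way; what is lost is the precision reported for it.

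Three conditions are needed: (a) the strata predict the trial transfer rate; (b) the allocation share is about the same in every stratum; (c) the variance is model-based.

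The plan gives indirect support for (a). It stratifies because facility rates differ widely, and 9.5 reports that "hospital transfer rates vary across facilities, even after adjusting for underlying patient risk", so the patient-level adjustment in 9.1 is not expected to absorb this variation. At stake is the width of the primary interval, and power if the true effect is below the planned range.

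**Working it through.** **1. Reproduce the plan's sample size.** Inputs from 9.2: rates 1.51 and 1.26 per person-year, 42 target residents per facility, 90% power, 103 facilities per arm. Assumed: two-sided 5% level and 42 person-years per facility. The between-facility coefficient of variation k is not given, so solve for it:

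103 = 1 + (1.96 + 1.2816)² × [(1.51 + 1.26)/42 + k²(1.51² + 1.26²)] / 0.25²

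102 × 0.0625 / 10.507 = 0.6067; 0.6067 − 0.0660 = 0.5408; 0.5408 / 3.8677 = 0.1398; k = 0.374.

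This k also returns the rest of the 1.51 row (165.5, 128.9 and 84.0 against 165, 129 and 84) and the 1.06 row. The 2.12 row needs k = 0.389.

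**2. Reported and true variance at 119/241.** Let R² be the share of between-facility variance explained by strata:

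V(c) = (λ₁/42 + c·k²λ₁²)/119 + (λ₀/42 + c·k²λ₀²)/241

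with c = 1 for the variance reported without strata and c = 1 − R² for the true variance. Under no effect (both rates 1.51), the within-facility term is 1.51/42 = 0.0360, the between-facility term is 0.374² × 1.51² = 0.3189, and 1/119 + 1/241 = 0.01255. The reported SE is √(0.3549 × 0.01255) = 0.0667, a 95% half-width of 0.131. Type I error = 2[1 − Φ(1.96 × √(V(1)/V(1 − R²)))].

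| Assumed R² | True SE | SE overstated | Correct half-width | Type I error, facility-rate formula | Type I error, zero-inflated mixed model |
|---|---|---|---|---|---|
| 0.1 | 0.0637 | 5% | 0.125 | 4.0% | 4.7% |
| 0.3 | 0.0570 | 17% | 0.112 | 2.2% | 3.2% |
| 0.5 | 0.0495 | 35% | 0.097 | 0.8% | 1.8% |

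The last column is a simulation of the planned type of model with a model-based Wald test; with strata it gave 5.2%. It was run separately and not repeated, but it is closest to the plan and should carry most weight.

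A facility-rate simulation (10,000 replicates; 33/33/32 of 99 and 7/7/7 of 21 facilities assigned to intervention) gave 4.3, 2.3 and 0.8% without strata and 5.4, 5.5 and 4.9% with. The estimate's empirical SD was 0.064, 0.057 and 0.049 in both analyses. At R² = 0 both gave 5.0%.

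**3. What R² implies.** Terciles keep (2/3) × (φ(0.431)/(1/3))² = 0.793 of a normal variable's variance. R² of 0.1, 0.3 and 0.5 therefore needs a correlation of √(R²/0.793), about 0.36, 0.62 and 0.79, between a facility's prior-year rate and its trial rate.

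**4. Less favourable inputs.** The 42 residents include patients outside fee-for-service, whom the primary analysis excludes; follow-up counts only days alive; and 9.5 calls the counts over-dispersed. Assuming 25 person-years and twice the Poisson variance (neither figure is in the documents), the within-facility term becomes 2 × 1.51/25 = 0.1208. The overstatement falls to 4, 13 and 25%, and type I error is 4.2, 2.7 and 1.4%.

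**5. Power, step 2 formula, without and with strata.**

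| Effect | R² 0.1 | R² 0.3 | R² 0.5 |
|---|---|---|---|
| 0.25 | 99.0 / 99.2% | 99.5 / 99.8% | 99.9 / 100.0% |
| 0.20 | 91.4 / 92.8% | 93.6 / 96.8% | 96.0 / 99.2% |
| 0.15 (illustrative, below the plan's range) | 67.6 / 70.9% | 69.5 / 80.0% | 72.1 / 89.6% |

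**6. Unequal allocation.** Let the intervention share be 0.331 − h, 0.331 and 0.331 + h across terciles with mean rates 1.51 − d, 1.51 and 1.51 + d, where d = √(1.5R²) × 0.374 × 1.51. The bias is 2hd / (3 × 0.331 × 0.669). At h = 0.02 it is 0.013, 0.023 and 0.029, and rejection stays below nominal (4.4, 3.3 and 2.1%). At h = 0.05 it is 0.033, 0.057 and 0.074, and rejection is 6.7, 9.8 and 12.4%.

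**7. Binary outcomes.** SE ratio = √{[ICC + (1 − ICC)/42] / [ICC(1 − R²) + (1 − ICC)/42]}. For assumed ICC of 0.01 to 0.10 and R² of 0.02 to 0.10, the SE is overstated by 0.3% to 4.4%.

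**The case against.** The strongest reply is that this is an efficiency preference. Under conditions (a) to (c) the planned analysis is valid and errs on the safe side. At the design effect of 0.25 the power cost is 0.3 points or less, and within the planned range it peaks at 3.2 points, at 0.20. That stands, and it fixes the severity.

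The size is also uncertain. The stratifier is an MDS hospitalization rate, while the outcome is claims-based transfers that include emergency visits and observation stays, so an R² of 0.5 is demanding. In a separate Poisson random-intercept simulation, a prior-to-trial correlation of 0.5 gave 4.9% rejection without strata (Monte Carlo error about 0.7 points), although its SE was still about 5% too large. At a correlation of 0.7 it gave 1.9%. This stands too.

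Adjustment is not perfectly free: that simulation rejected 5.5 to 6.5% with strata at correlations of 0.5 to 0.9, slightly above nominal. This is a reason to state the variance method, not to leave the strata out.

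A reader might infer from the précis that the sponsor deliberately excludes strata. The sentence more naturally rules out stratum-specific analyses; it leaves open whether strata enter the model. Strata are unspecified, not expressly rejected.

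**Conclusion.** The concern holds as a minor point. The primary model omits the six strata and no section supplies them. Under (a) to (c) the primary interval is too wide and the test conservative. The amount is unknown because the documents give no R². For R² of 0.1 to 0.5, type I error runs from about 4.7% down to 1.8% in the zero-inflated model. The 5 to 35% overstatement from the facility-rate formula is an upper bound for those values.

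Two stronger readings are not supported. One is that the trial loses its planned power: without strata, power in step 5 stays at about 90% or more from 0.20 to 0.275 (90.4% at 0.20 even if R² = 0). The other is that the primary result is biased or prone to false positives: that needs a material difference in allocation share between strata, and the documents do not show one. They do not rule it out either, so the conservative direction depends on (b).

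The practical value lies in smaller effects. Section 9.6 reports that only 12.5% and 31.4% of long-stay residents in the two systems had been shown a video, which makes an effect below the planned range plausible. For the binary secondary outcomes the consequence is likely negligible.

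**What to change.** Before arm-level outcomes are seen:

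- In 9.5, pre-specify fixed effects for the six strata in both parts of the primary model.
- Estimate each arm's marginal rate by averaging predictions over the strata, weighted by stratum size. Test that standardised difference and state how its variance is computed.
- For consistency, add the strata to the secondary logistic models. For advance directives, which Section 1 restricts to certain Genesis facilities, use the Genesis terciles only.
- In 4.4.3, state the allocation within each stratum.
- Reword the précis sentence to say that strata are in the model and that no stratum-specific effects are planned.

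The cost is SAP text, using strata that already exist. It adds 10 parameters to the primary model (5 per part), 5 to each logistic model and 2 for advance directives, with 360 facilities overall. As a guide, in a facility-level analysis the t critical value moves only from 1.9666 (358 df) to 1.9667 (353 df). The small downside is that the logistic odds ratios become conditional on stratum. If the strata predict nothing, essentially nothing is lost.

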9.2. Sample Size and Randomization

Sample size estimates are based on the primary trial outcome: # hospital transfers/person-days alive based on Medicare claims data), which include admissions, emergency department visits, and observation stays over a 12-month follow-up period among Medicare fee-for-service long-stay residents with advanced dementia or advanced COPD/CHF. Based on data from our partners' NHs in 2012 and 2013, we estimate that hospital transfers per person-year alive in the control arm will be between 1.06 and 2.12. Based on prior research; we estimate the absolute reduction in hospital transfer rates in the intervention vs. control NHs will range from .200 to .275 points, representing approximately a 16% relative reduction.

| Initial Hospital Transfer Rates/Year | Effect Size | | | |
|--------------------------------------|-------------|-------|------|-------|
| | 0.20 | 0.225 | 0.25 | 0.275 |
| 1.06 | 81 | 63 | 50 | 41 |
| 1.51 | 165 | 129 | 103 | 84 |
| 2.12 | 351 | 275 | 220 | 180 |

Computations for sample size estimates were performed using the approach for the comparison of incidence rates discussed in Chapter 5 of Donner & Klar and in Hayes & Bennett (1999). The sample size computation is based on a simplifying assumption of a Poisson distribution for the numbers of hospital transfers, and it assumes equal number of facilities in each arm. To achieve power of at least 90% in testing for

a .25 point absolute reduction in the observed average hospital transfer rate of 1.51, we will require 103 facilities per study arm. This represents approximately a 16% relative reduction in the hospital transfer rate.

Although our sample size calculations indicate that we require 103 NHs/arm, to accommodate the anticipated 10% non-participation rate among NHs randomized to the intervention arm, we will recruit an additional 16 facilities in the intervention arm for a total of 119 intervention NHs. Moreover, because there is an available total pool of 360 eligible facilities in our partner health systems, we will choose to assign the remaining 241 facilities to the control arm (approximate 2:1 control:intervention match) since there is no additional cost to do so. While more control facilities only marginally increases power it allows for a more precise estimate of the outcome of interest in the control group.

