advanced dementia or advanced CHF/COPD. Outcomes include: advance directives during their NH stay, the number of hospital transfers over 12-months for long-stay or over 100 days for short-stay; and hospice admission over 12 months for long-stay or over 100 days for short-stay. As hospital transfers and hospice enrollment among post-acute care patients are likely to occur after NH discharge, these outcomes can only be assessed among the fee-for-service Medicare beneficiaries using Medicare claims. The outcome, Y_{ij} , is a total count of hospital transfers. Many relatively healthy patients will have $Y_{ij}=0$ while others' hospital use depends on the number of days that they are alive. We will use a zero-inflated Poisson model^{135, 136} of the following form shown in the equation, where $\text{logit}(\pi_{ij}) = X_i\beta + \eta T_i + \delta_{ij}$, X_i are the covariates, η is the treatment effect, and $\varepsilon_{ij} \sim N(0, \sigma_\pi)$ is a random between facility effect. When η is larger than 0 and λ is smaller than 0, ACP video is effective. The same analytic approach described for Aim 2 will be used to evaluate the effectiveness of the intervention.

Sub-Group Analyses of Racial and Ethnic Group Differences in Intervention Effects: It is well-recognized that African-American NH patients with advanced illness are more likely than white patients to have outcomes reflecting more aggressive care, including higher hospitalization rates and lower advance directive documentation rates, even after controlling for patient and facility factors. Nonetheless, there is no evidence suggesting that African American patients respond differently to our ACP intervention than white residents. In fact, the videos have been specifically designed to be appropriate to viewers from all backgrounds

Based on existing data, we anticipate only 11% of the patients included in our analyses will be African-American, and even lower proportions will be of other non-white racial and ethnic groups. Thus, there will not be sufficient power to detect small differences in outcomes among non-white groups. Consequently, these sub-group analyses are necessarily exploratory. Nonetheless, we will conduct sub-group analyses for Aim #2 separately among African-American residents and other racial/ethnic groups (e.g., Hispanic) if numbers allow. Additionally, we will examine differences in video viewing rates among racial and ethnic groups.

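### The racial and ethnic subgroup plan specifies separate Aim 2 analyses in each group but no estimate or test of a difference in intervention effect

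*Combined protocol and SAP*

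**What the plan says.** The subsection of Section 9.5 is titled "Sub-Group Analyses of Racial and Ethnic Group Differences in Intervention Effects". It notes that African-American residents with advanced illness tend to receive more aggressive care, and that there is no evidence that they respond differently to the videos. It then says that "we will conduct sub-group analyses for Aim #2 separately among African-American residents and other racial/ethnic groups", subject to numbers.

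The same subsection states its limits: "we anticipate only 11% of the patients included in our analyses will be African-American", "even lower proportions will be of other non-white racial and ethnic groups", "there will not be sufficient power to detect small differences in outcomes among non-white groups" and "Consequently, these sub-group analyses are necessarily exploratory".

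The Aim 2 model equations in Section 9.5 contain the treatment indicator, facility random effects and, for the primary outcome, the log of person-days alive. They have no race term and no treatment-by-race term, and no other section adds a between-group contrast. The subsection also plans to compare video viewing rates across groups, but that concerns exposure, not effect.

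**The concern.** The title asks whether the effect differs between groups. An analysis run inside one group estimates the effect in that group. Two such analyses side by side do not give the difference between the effects, its standard error or a test.

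The practical risk is misreading. The smaller group has the larger standard error, so it will more often miss significance even when the videos work equally well in everyone. Section 2.2 names racial disparities in advance directives as a serious concern, and Section 2.4 cites findings that the videos reduce disparities. An apparent failure in African-American residents that reflected only their number would bear directly on that question.

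**Working it through.** **Inputs from the plan.** Control rate 1.51 transfers per person-year, a reduction of 0.25 (range 0.20 to 0.275), 103 facilities per arm, 42 target residents per facility (Section 9.2); 119 intervention and 241 control facilities (Sections 4.4.2 and 9.2); 11% share (Section 9.5). The sizing sentence opens "To achieve power of at least 90% in testing for" that reduction, and for the primary comparison the plan says "We will use a two sided test to examine if the marginal average difference is significantly different than zero".

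**Assumptions.** Two-sided alpha 0.05 (no level is stated). A full person-year per resident. African-American residents spread evenly, so 42 × 0.11 = 4.62 per facility against 37.38 others. The same control rate and the same true effect in both groups. The comparison group is all remaining residents. Simple rate differences with a normal approximation stand in for the zero-inflated model.

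**1. The plan's 103.** The formula for comparing cluster incidence rates is

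c = 1 + (1.960 + 1.282)² × [(λ0 + λ1)/y + k²(λ0² + λ1²)] / (λ0 − λ1)².

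The between-facility coefficient of variation k is not given, so 103 cannot be checked independently. Setting c = 103, λ0 = 1.51, λ1 = 1.26 and y = 42 gives k² = [102 × 0.0625/10.507 − 2.77/42] / 3.868 = 0.140, so k = 0.374. No single k reproduces every cell of the plan's table; the best fit, about 0.38, is 4% to 5% low in the 2.12 row.

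**2. Variances at a reduction of 0.25, pure Poisson.**
- Sampling, African-American residents: 1.26/(4.62 × 119) + 1.51/(4.62 × 241) = 0.00365
- Sampling, other residents: 1.26/(37.38 × 119) + 1.51/(37.38 × 241) = 0.00045
- Facility: 0.374² × (1.26²/119 + 1.51²/241) = 0.00319

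The subgroup standard errors are √(0.00365 + 0.00319) = 0.083 and √(0.00045 + 0.00319) = 0.060. If both groups carry the same facility effect, the two estimates have correlation 0.00319/(0.0827 × 0.0603) = 0.64.

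**3. Disagreement on significance with identical true effects.** Power is 86% in African-American residents and 99% in the others. From the bivariate normal, both are significant in 85.3% of trials. Disagreement is 85.6% + 98.6% − 2 × 85.3%, or about 14%.

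| Reduction | Over-dispersion factor | Power, 11% group | Power, others | Disagree |
|---|---|---|---|---|
| 0.275 | 1 | 92% | 99.6% | 8% |
| 0.25 | 1 | 86% | 99% | 14% |
| 0.20 | 1 | 66% | 90% | 28% |
| 0.25 | 2 | 69% | 97% | 30% |
| 0.25 | 3 | 56% | 96% | 42% |

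Factors 2 and 3 are assumed: Section 9.5 reports over-dispersion without a figure. Nearly all the disagreement runs one way. At 0.25 with factor 1, 13.3 of the 13.6 percentage points are trials where the others are significant and the 11% group is not.

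**4. Sensitivity.** Halving person-years per facility to 21, to reflect deaths or the fee-for-service restriction, gives 30% at 0.25 with factor 1. A group with an assumed 5% share gives about 34%, 55% and 65% at 0.25 for factors 1, 2 and 3. At a quarter of the design effect, disagreement is about 15% to 16%.

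**5. Standard error of the group difference (0.25, factor 1).** With the facility effect fully shared it cancels: √(0.00365 + 0.00045) = 0.064. With none shared: √(0.00365 + 0.00045 + 2 × 0.00319) = 0.102.

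**6. What an interaction test would do.** In simulations of 4,000 trials per setting (negative-binomial counts, shares of 11% and 5%, full and half effect, identical effects in both groups), it declared a difference in 4.9% to 5.9% of trials. In the same trials the separate analyses disagreed in about 38% to 62%. At an 11% share and factors 1 to 3, it has 80% power only for a difference in effect of 0.18 to 0.31 (facility effect shared) or 0.29 to 0.38 (not shared), against a whole design effect of 0.25.

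**The case against.** The strongest reply is that the plan never says significance will be compared across groups. It states no decision rule and poses no hypothesis of a differential effect. Group-specific estimates with intervals are a legitimate descriptive output, and the paragraph already warns of low power and calls the work exploratory. All of that stands and keeps the point minor. It does not supply the missing contrast: the caveat limits how firmly results may be claimed, but it does not answer the question in the title.

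A reader might infer more than the documents support in three ways.

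- That the plan intends to judge differences by setting one p-value against another. The text does not say so; the supportable defect is an omission.
- That conflicting significance is the usual result. At the design effect under pure Poisson variation it is about 14%, and at 0.275 about 8%. Higher figures need a smaller effect, a smaller group, fewer person-years or an over-dispersion factor that the plan does not give.
- That a single model certainly cuts the standard error from 0.102 to 0.064. That needs African-American residents mixed evenly within facilities and a facility effect common to both groups, and the documents show neither. Nor can 0.064 be paired with disagreement rates for independent groups: at 0.20 independence gives 37%, while the sharing that produces 0.064 gives 28%.

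It is also fair to say that the remedy gains little power, as step 6 shows.

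**Conclusion.** The concern holds as an omission of minor severity. Section 9.5 sets out to examine differences in effect and specifies no estimate or test of one. On the plan's inputs and the assumptions listed, separate analyses of truly identical effects disagree on significance in about 8% to 28% of trials across the plan's effect range under pure Poisson variation, and in about 30% to 42% at 0.25 with over-dispersion factors of 2 to 3. The standard error of the group difference lies between 0.064 and 0.102. These sizes rest on an unstated alpha, a back-calculated k, even spread, a common control rate and full follow-up; the omission itself rests on none of them.

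**What to change.** In Section 9.5, replace separate fitting with one Aim 2 model that includes race/ethnicity and a treatment-by-race/ethnicity interaction. For the zero-inflated primary model, put these terms in both the zero part and the count part. Then obtain the marginal rate difference between arms in each group and the contrast between those differences, with its confidence interval. State the scale: the plan expects higher hospitalization in African-American residents, so absolute and relative contrasts may differ. Report group-specific effects from the same model, and keep the exploratory label and the power caveat.

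The cost is a few lines of SAP wording and a little extra analysis. Race and ethnicity are already among the MDS elements in Section 6.3.2, so no new data are needed and the primary analysis is unchanged. The drawback is that the interaction estimate will be imprecise, which its interval will show.
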